2.6. Trial quality statement

The trial will be conducted in accordance with the Protocol, in strict compliance with applicable regulatory requirements, including but not limited to:

- Constitution of the Russian Federation;
- Current version of the Federal Law of the Russian Federation dated 21 November 2011 No. 323-FZ "On the Fundamentals of Health Protection of Citizens in the Russian Federation";
- Current version of the Federal Law of the Russian Federation No. 61-FZ "On Circulation of Medicines" dated 12 April 2010;
- Current version of the Federal Law of the Russian Federation dated 27 July 2006 N 152-FZ "On Personal Data"
- Order of the Ministry of Health of the Russian Federation No. 200 n of 01.04.2016. "On Approval of the Rules of Good Clinical Practice";
- Russian National Standard GOST R 52379-2005 "Good Clinical Practice", which complies with the standards of the International Conference on Harmonisation of Technical Requirements for Registration of Pharmaceutical Products for Human Use (ICH) Good Clinical Practice Guidelines (ICH-GCP);
- Rules of Good Clinical Practice of the Eurasian Economic Union, approved by the Decision of the Council of the Eurasian Economic Commission dated 03 November 2016 No. 79;
- The Rules of Compulsory Life and Health Insurance for Patients Participating in Clinical studies of a Medicinal Product approved by Resolution of the Government of the Russian Federation No. 714 dated 13 September 2010;
- Resolution of the Government of the Russian Federation No. 393 dated 18 May 2011 "On Amendments to the Model Rules for Compulsory Life and Health Insurance for Patients Participating in Clinical studies of a Medicinal Product";
- Rules of the International Conference on Harmonisation of Technical Requirements for Registration of Medicinal Products for Human Use;
- The World Medical Association's 1964 Declaration of Helsinki, most recently revised (Fortaleza, 2013);
- Guidelines for Expertise of Medicinal Products of FGBU NCESMP of the Ministry of Health of Russia (Moscow, 2013)
- Order of the Federal Service for Healthcare Oversight No. 1071 dated 15.02.2017 "On Approval of the Procedure for Pharmacovigilance";
- Order of the Ministry of Health and Social Development of the Russian Federation No. 757n dated 26.08.2010 "On Approval of the Procedure for Monitoring the Safety of Medicinal Products for Human Use, Registration of Adverse Actions, Serious Adverse Reactions, Unexpected Adverse Reactions in the Use of Medicinal Products for Human Use";

The clinical trial will be conducted in accordance with the current version of the Trial Protocol. The Protocol and any amendments to the Protocol and the Patient Information Sheet with the Informed Consent Form must be approved/endorsed by the regulatory authorities, the Ethics Council and the Local Ethics Committee.

2.7. Description of the trial population

The calculation of the required sample size for this trial is scientifically and statistically sound and meets the requirements for efficacy and safety studies in the Russian Federation.

The inclusion criteria for volunteers are scientifically justified. It is planned to include in

the trial patients differing in the degree of severity of neurological deficit (Functional Status Score on the modified Rankin Scale (mRS) of 3 and more points, NIHSS score from 9 to 15 points inclusive), which will bring the results obtained in the clinical trial closer to real clinical practice and will allow to assess efficacy of the investigational therapy in the population of patients with severe neurological deficit.

A maximum of 336 patients with diagnosed hemispheric ischaemic stroke are planned to be included in the trial (obtain approval for a clinical trial involving 336 **patients**), from which **at least 304 patients** with a clinically confirmed diagnosis of hemispheric ischaemic stroke meeting the inclusion criteria and no non-inclusion criteria are planned to be **randomized**.

The selection criteria for this trial were carefully considered to ensure patient safety and the validity of the results of this trial.

- 37. Shchulkin A. B. Effect of mexidol on the development of the phenomenon of neuronal excitotoxicity in vitro // Journal of Neurology and Psychiatry. SS Korsakov. - 2012. - V. 112. - №. 2. - P. 35-39.

3. Purpose and objectives of the trial

3.1. Trial purpose:

The aim of the present trial was to compare the efficacy and safety of sequential therapy with Mexidol® solution for intravenous and intramuscular administration, 50 mg/ml (RPC PHARMASOFT LLC, Russia) and Mexidol® FORTE 250 film-coated tablets, 250 mg (RPC PHARMASOFT LLC, Russia) compared with placebo during their sequential administration in patients in the acute and early recovery periods of ischaemic stroke.

3.2. Trial objectives:

- 1. To evaluate the efficacy of the preparations Mexidol® solution for intravenous and intramuscular injection, 50 mg/ml (RPC PHARMASOFT LLC, Russia) and Mexidol® FORTE 250 film-coated tablets, 250 mg (RPC PHARMASOFT LLC, Russia) during their sequential use in patients in the acute and early recovery periods of ischaemic stroke vs. placebo.
- 2. To carry out a comparative evaluation of the frequency and severity of adverse events of the preparations Mexidol® solution for intravenous and intramuscular injection, 50 mg/ml (RPC PHARMASOFT LLC, Russia) and Mexidol® FORTE 250 film-coated tablets, 250 mg (RPC PHARMASOFT LLC, Russia) during their sequential use in patients in the acute and early recovery periods of ischaemic stroke vs. placebo.

4. Trial design

4.1. Main and additional trial parameters to be assessed in the course of the trial

In accordance with the purpose and objectives of the trial, this clinical trial will determine the parameters of comparative efficacy and safety of Mexidol® solution for intravenous and intramuscular administration, 50 mg/ml (RPC PHARMASOFT LLC, Russia) and Mexidol® FORTE 250 film-coated tablets, 250 mg (RPC PHARMASOFT LLC, Russia) vs. placebo when used in patients in the acute and early recovery periods of ischaemic stroke.

The efficacy of the investigational therapy will be assessed by the following parameters:

Primary efficacy criterion:

- The magnitude of change in the patient's **mRS** (Modified Rankin Scale) score at the end of therapy vs. baseline (in points).

Secondary efficacy criteria:

- The magnitude of change in the patient's **mRS** (Modified Rankin Scale) score at the end of parenteral therapy vs. baseline (in points).
- Proportion of disabled patients (**mRS** score 3 or more) at the end of therapy;
- Proportion of disabled patients (**mRS** score 3 or more) at the end of parenteral therapy;

- Proportion of patients with mRS score 0-1 at the end of therapy;
- Proportion of patients with mRS score 0-1 at the end of parenteral therapy;
- The magnitude of change in the patient's **NIHSS** (National Institutes of Health Stroke Scale) score at the end of therapy vs. baseline (in points).
- The magnitude of change in the patient's **NIHSS** (National Institutes of Health Stroke Scale) score at the end of parenteral therapy vs. baseline (in points).
- The magnitude of change in the patient's **MoCA** cognitive status score at the end of therapy vs. baseline (in points).
- The magnitude of change in the patient's **MoCA** cognitive status score at the end of parenteral therapy vs. baseline (in points).
- The magnitude of change in the patient's **Rivermead** Mobility Index score at the end of therapy vs. baseline (in points).
- The magnitude of change in the results of the patient's state assessment by the **Rivermead** mobility index at the end of the parenteral course of therapy vs. baseline (in points).
- The magnitude of change in the patient's **HADS** score at the end of therapy vs. baseline (in points).
- The magnitude of change in the patient's **HADS** score at the end of parenteral therapy vs. baseline (in points).

Safety and tolerability will be assessed throughout the trial (from first use of the investigational product/placebo) using the following data:

- AE/SAE reports data,
- Physical examination data, vital signs (BP, HR, respiratory rate, body temperature),
- Indicators of laboratory analyses and instrumental methods of examination.

A conclusion on the safety of the investigational product will be made after statistical evaluation of all AEs, including serious SAs with at least a possible association with the use of the investigational product.

4.2. Description of the type/design of the trial

This trial is a prospective multicentre, randomized, double-blind, parallel-group comparative trial of the efficacy and safety of Mexidol® solution for intravenous and intramuscular administration, 50 mg/ml (RPC PHARMASOFT LLC, Russia) and Mexidol® FORTE 250 film-coated tablets, 250 mg (RPC PHARMASOFT LLC, Russia) when administered sequentially in patients in the acute and early recovery periods of ischaemic stroke vs. placebo.

The trial is carried out during the inpatient follow-up of patients and as part of patients' outpatient visits to the investigational site.

After screening, patients fulfilling inclusion criteria and those without inclusion criteria were randomly allocated into two groups (1:1 patient-to-patient ratio):

Group I - use of preparations Mexidol® solution for intravenous and intramuscular injection, 50 mg/ml (RPC PHARMASOFT LLC, Russia) 10 ml (500 mg) BID (1000 mg per day) intravenous drip in 100-200 ml 0.9% NaCl solution for 10 days and Mexidol® FORTE 250 film-coated tablets, 250 mg (RPC PHARMASOFT LLC, Russia) 1 tablet TID for the next 60 days.

Group II - use of Placebo 1, solution for intravenous and intramuscular injection 10 ml BID by intravenous drip in 100-200 ml of 0.9% NaCl solution for 10 days and Placebo 2, film-coated tablets, 1 tablet TID for the next 60 days.

The use of investigational products is carried out against the background of standard therapy of ischaemic stroke prescribed by the patient's attending physician.

The trial will include the following periods:

- **Screening** - preliminary examination of patients. The duration of the period should not be

more than 24 hours. Screening, randomization and initiation of therapy can be done on the same day.

- **Randomization and initiation of therapy** - randomization, initiation of trial therapy.
- **Therapy period** (70 days in total), use of investigational product/placebo (10 days - parenteral administration period, 60 days - oral administration), patient assessment, registration of AEs.

The graphical scheme of the trial is shown in Figure 4.1.

[figure not shown]

Figure 4.1. Graphical design of the trial

4.3. Measures to minimise/eliminate subjectivity in the conduct of the trial

4.3.1. Blinding

The present trial is a double-blind trial. The double-blind method avoids bias, subjectivity in the evaluation of treatment results. The patient participating in this trial, the Investigator, and the clinical diagnostic laboratory staff will not be aware of which of the medicinal products the patient is taking. In this regard, blinded primary and secondary investigational product/placebo packaging is provided.

4.3.2. Randomization

After the patient (his/her legal representative) signs the Informed Consent Form at the screening stage, he/she is assigned a screening number of the form XXXYYYY, where XX is the number of the investigational site (e.g. 01, 02, 03), YYY is the patient's serial number (starting from 001), according to the order of inclusion (3 digits). If, after all the procedures planned as part of the screening, the investigator decides that the patient can take part in the trial, the patient is randomized.

randomization (an allocation method according to probability theory) is necessary to minimise subjectivity in assigning patients to therapy groups.

The randomization code will be presented in a three-digit format of the form RRR and will be assigned to each screened patient who meets the inclusion/non-inclusion criteria.

Allocation of patients to therapy groups will be done in a 1:1 ratio.

The randomization procedure, assigning a randomization number to the patient will be done after all screening procedures have been carried out before prescribing the IP.

The randomization code of each patient must be compulsorily recorded in the patient's source documentation and CRF.

If a patient early terminates the trial (is excluded from the trial for any reason), his/her randomization code will not be reused.

Randomization will be carried out centrally. For the implementation of centralized randomization (electronic randomization system) it is planned to use an automated communication system over the Internet - Interactive Web Response System (IWRS). Once the Investigator enters the patient data, the number will be generated automatically by the system.

4.4. Expected duration of patient participation in the trial

The total duration of patient participation in the trial will be no more than 74 days, including the screening period.

The trial will include the following periods and visits:

- **Screening** (Visit 0) - pre-screening of patients.

The duration of the period should not be more than 24 hours from the time of the informed consent procedure to randomization. Screening, randomization and initiation of therapy can be done on the same day.

- **Randomization and initiation of therapy** (Visit 1) - randomization of patients, initiation of trial therapy.

- **Therapy period** (Visits 2-4, Phone calls), use of investigational product/placebo (Duration of therapy - 70 days: 10 days - period of parenteral administration, 60 days - oral administration), assessment of the patient's condition, registration of AE. The total patient period, including scheduled procedures, is 71 (+2) days.

4.5. Suspension, termination of the trial, termination of participation in the trial by individual subjects

The sponsor has the right to temporarily suspend the trial at any time for reasons including, but not limited to, safety, ethical, or administrative issues.

The sponsor has the right to terminate the trial at any time if the goals and objectives of the trial are not being met.

In doing so, the Sponsor must notify the Investigator or the management of the investigational site of the temporary suspension or early termination of the trial in writing.

If the trial is suspended or terminated for safety reasons, the Sponsor will immediately inform the Investigator, as well as regulatory authorities and ethics committees.

The Investigator has the right to terminate participation in the trial (withdraw from the trial) of individual subjects when exclusion criteria are found.

4.6. Investigational product/comparator product record-keeping procedures

The Investigator is responsible for following certain rules for handling investigational products:

- Maintains records of receipt of investigational product/comparator product.
- Maintains records of investigational product/comparator product consumption at the investigational site using the investigational site's drug record form. The investigational product/comparator product should only be given to those members of the investigational site team whose responsibility it is to keep track of the medicines. The allocation of responsibilities is recorded on a special form before the trial begins.
- Ensures that the investigational product/comparator product is administered in strict accordance with the Protocol, i.e. only to those patients who are included in the trial and randomized.
- Ensures that preparations are stored in accordance with the Protocol or other supplemental instruction that includes information on storage conditions of the preparation. The Investigator should regularly record the temperature readings in the room where the preparations are stored, except on weekends and public holidays, and record them in a special logbook of the storage temperature of the preparations.
- Records the IP returned to the Sponsor by completing designated documentation. Unused IP, as well as packaging from used IP, will be returned to Sponsor for destruction.
- All unused medications as well as packs of used medications should be collected for compliance assessment. Compliance will be assessed by the Investigator. The reasons why compliance was not observed should be ascertained by the Investigator wherever possible.

4.7. Storage and disclosure of randomization /screening numbers

The double-blinding condition is observed throughout the trial. The randomization code for a particular patient should be prematurely disclosed in the following cases:

- occurrence of an insured event, if the qualification of the event requires information about the type of prescribed therapy;
- sponsor's decision;
- written request from the local ethics committee supervising the trial;
- decision of regulatory authorities (Ministry of Health, Ethics Council under the Ministry of Health of the Russian Federation, Federal Service for Surveillance in Healthcare, other regulatory body authorized in accordance with the established procedure to control the conduct of clinical studies).

If it is necessary to disclose the code, the investigator performs the unblinding procedure according to the instructions received prior to the trial.

A complete list of all screening/randomization numbers used in the trial and their corresponding therapy is a confidential document, kept by the authorized representative and used to monitor the conduct of the trial.

The Investigator should ensure that the anonymity of the patients is respected. In the CRF, patients are identified only by assigned numbers.

The Investigator must maintain documentation containing patient number information, stored in accordance with the rules applicable to confidential documents.

The Investigator must also maintain in strict confidence documents not intended to be handed over to the Sponsor, particularly signed Patient Information Sheets with the Informed Consent Forms.

4.8. A list of all data recorded directly in the CRF and considered as source data

This trial does not contain data to be entered directly into the CRF without initially recording such information in source documentation.

All information that is recorded in the CRF is previously entered into the patient's source medical documentation - the patient's medical record, blood and urine laboratory test forms, ECG forms, etc. An electronic data collection system can also be used to collect source data (e.g. results of specialized scales).

5. Selection and exclusion of trial participants

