APPENDIX 3.

**NIHSS (The National Institutes of Health Stroke Scale)
Example form**

INSTRUCTIONS

- Assess the scale items in the sequence indicated.
- Record the result for each item of the scale immediately after the corresponding survey.
- Do not go back to the preceding paragraphs or change the assessment.
- Follow the instructions provided for each examination procedure.
- The assessment should reflect what the patient does, not what the Investigator thinks the patient is capable of doing.
- The Investigator should record results as the survey progresses and work quickly.

Unless indicated, the patient should not be forced to perform the test (e.g., repeating a question to the patient to get his/her attention)

IF ANY SECTION OF THE SCALE WAS NOT TESTED, THE INVESTIGATOR MUST PROVIDE A DETAILED WRITTEN EXPLANATION OF THE REASON. ALL UNTESTED SECTIONS OF THE SCALE WILL BE REVIEWED BY THE CLINICAL RESEARCH ASSOCIATE AND DISCUSSED WITH THE INVESTIGATOR IN PERSON OR BY TELEPHONE

INSTRUCTIONS	Scale description	Scores
1a. Level of consciousness: The investigator should assess the patient's level of consciousness even if a complete examination is not possible due to obstacles such as an endotracheal tube, language barrier, orotracheal trauma or bandage. A score of 3 is given if the patient does not demonstrate a motor response (other than a reflexive change of posture) in response to pain stimulation	0 = Clearly conscious; responds quickly. 1 = Unconscious, but with minimal stimulation it is possible to execute a command, receive a verbal response or reaction. 2 = Unconscious, repeated stimulation is required to elicit a response, or the sense of pain is blunted and strong or painful stimulation is required to elicit a motor response (not stereotyped). 3 = Response only in the form of a reflex motor or autonomic nervous system response, or the patient is unresponsive, has decreased muscle tone and no reflexes	

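### Section 4.7 has the investigator perform every code break, although no listed ground, as stated, requires the site to know the arm, and neither document says how later scores are handled

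*Protocol*

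**What the plan says.** Protocol section 4.7 lists four grounds for opening a patient's code early:

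- "occurrence of an insured event, if the qualification of the event requires information about the type of prescribed therapy";
- "sponsor's decision", with no purpose or limit given;
- "written request from the local ethics committee supervising the trial";
- a decision of a regulatory authority.

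The section then assigns the step to the site for every ground: "If it is necessary to disclose the code, the investigator performs the unblinding procedure according to the instructions received prior to the trial". Those instructions are a separate document. The same section says that the complete list of numbers and treatments is confidential, "kept by the authorized representative and used to monitor the conduct of the trial". Section 4.3.2 describes central randomization through an IWRS.

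Section 4.3.1 rests the control of subjectivity on blinding: "The patient participating in this trial, the Investigator, and the clinical diagnostic laboratory staff will not be aware of which of the medicinal products" a given patient receives. It names no separate outcome rater.

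mRS is scored at Visits 0, 2 and 4 (section 6.3.11). Sections 6.2, 6.3.11 and 7.2 and the mRS form in Appendix 2 do not say who scores it. The NIHSS instructions in Appendix 3 do name the examiner: "The Investigator should record results as the survey progresses and work quickly". The MoCA guidance in Appendix 4 also names the investigator.

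The per-protocol (PP) set, which is primary for efficacy, consists of patients who completed in line with the protocol (Protocol 9.6 and 9.7.2; SAP section 11). Code breaks appear neither in that definition, nor in the exclusion criteria (5.3), nor among the example significant deviations (11.8).

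**The concern.** Each listed ground comes from, or serves, a party outside the treating site: an insurer, the sponsor, an ethics committee or an authority. That party can be told the arm without the site learning it. Section 4.7 nevertheless sends every disclosure through the person whose blinding section 4.3.1 relies on.

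mRS is a judgement-based score, and the planned difference is small: 0.292 point against a superiority boundary of 0.027. If the rater knows the arm, later scores are open to expectation bias in the direction of the hypothesis. The investigator also judges causality of adverse events (8.3) and may withdraw patients by judgement (5.3, items 3 to 5). With a PP primary analysis, knowledge of the arm could therefore affect both the score and who is counted.

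**Working it through.** **1. Does any ground, as written, need the site to know?**

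| Ground in 4.7 | Who originates or uses it | Site need stated? |
|---|---|---|
| Insured event | Insurer, to classify the event | No |
| Sponsor's decision | Sponsor; purpose open | No, but not ruled out |
| Ethics committee request | Local ethics committee | No |
| Regulatory decision | Authority | No |

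The list holder (4.7) and the IWRS (4.3.2) suggest that a route past the site is available.

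**2. Can the rater be the person unblinded?** The investigator is the named examiner for NIHSS and MoCA. For mRS the rater is unnamed and no independent rater is provided, so the investigator is the probable rater by inference. Because mRS is scored at Visits 2 and 4, a break after Visit 1 can precede either score, and Visit 4 supplies the primary endpoint.

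**3. What happens to later scores?** A disclosure made under 4.7 follows the protocol, so it is not in itself a deviation. With no mention in 5.3, 9.6, 11.8 or SAP section 11, a patient who completes stays in the PP set by default. No flag or sensitivity analysis for such scores is planned.

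**4. Size, for illustration.** Inputs from Protocol 9.1: SDs 0.755 and 0.847, ε = 0.292, δ = 0.027, one-sided α = 0.05, power 80%.

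The plan's own figure first:

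- Pooled SD = √((0.755² + 0.847²)/2) = 0.802.
- n per group = 2 × (1.6449 + 0.8416)² × 0.802² / (0.292 − 0.027)² = 113.25, rounded up to 114. Then 2 × 114 = 228, and 228/0.75 = 304.

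The stated sample size reproduces, and this point does not change it.

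Standard error of the difference with 114 per group: 0.802 × √(2/114) = 0.1062.

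If m patients in an arm are scored b points towards expectation, the difference moves by m × b/114, or by 2 × m × b/114 if both arms move in opposite directions. When the true difference equals δ, the one-sided error becomes Φ(bias/0.1062 − 1.645). Both m and b are assumptions; neither document gives them.

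| Assumed m | Assumed b | Bias (points) | One-sided error |
|---|---|---|---|
| 1, Mexidol arm only | 0.5 | 0.5/114 = 0.0044 | 5.4% |
| 1 per arm, opposite directions | 0.5 | 2 × 0.5/114 = 0.0088 | 5.9% |
| 3, Mexidol arm only | 1 | 3/114 = 0.0263 | 8.1% |
| 3 per arm, opposite directions | 1 | 2 × 3/114 = 0.0526 | 12.5% |

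The last row is a worst case. Three per arm roughly matches the serious-event rate of the earlier EPICA trial (section 2.3.2: 4 in 150, or 2.7%; 0.027 × 114 ≈ 3). It requires that every such event leads to a code break before Visit 4, that every such patient stays in the PP set, and that every score moves a full point.

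**The case against.** Three stronger readings are tempting, and the documents support none of them.

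- *The person who breaks the code rates the primary outcome.* No section names the mRS rater; the forms that name the investigator are for secondary endpoints. Investigator rating is likely, but it is inferred.
- *Post-break scores are certain to count.* No text says so. The deviations in 11.8 are only examples, and items 3 to 5 of 5.3 allow discretionary withdrawal, which would take a patient out of the PP set. What stands is that the documents are silent and that the default is inclusion.
- *Every disclosure to the site is needless, and the error rises to 6–13%.* The sponsor's ground has no stated purpose and could cover a case where the site must know. The separate instructions may limit who sees the result. Serious events overstate code breaks, because the insured-event ground applies only where classification needs the treatment, and patients with serious events are among those most likely to leave the PP set.

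A further objection concerns the remedy. A rule that the site stays blind on all four grounds without exception could close the only listed ground on which a treating site might learn the allocation. That is correct, and the fix below is limited accordingly. It is also fair that 4.7 does not say whose representative holds the list.

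The core remains. Assigning the step to the investigator is an explicit rule in 4.7, stated without exception, and the absence of any handling rule for later scores is common to both documents.

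**Conclusion.** The point holds in a limited form. Section 4.7 routes every premature disclosure through the investigator although its grounds, as stated, do not require the site to know. This can unblind the probable mRS rater before Visit 2 or Visit 4, and neither document flags or handles the scores that follow. The conclusion rests on one inference (that the investigator scores mRS) and on silence about later scores.

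The effect is likely to be small because few patients should be affected. No figure for bias or type I error can be derived from the documents alone. The 5.9% for one patient per arm shows the order of magnitude if breaks are rare; the higher values in the table should not be quoted as expected results. Severity is minor: this is a cheap improvement.

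**What to change.** - Amend 4.7 so that, by default, the code is released by the list holder or through the IWRS directly to the requesting party, without disclosure to the investigator, site staff or patient, unless the request itself requires the site to know. Align the unblinding instructions and identify the list holder's role.
- Log the date, reason and recipients of every code break.
- Flag mRS and NIHSS scores obtained after a site learns the arm, and pre-specify in the SAP one sensitivity analysis of the primary endpoint without them.

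The cost is one change of procedural wording, a log, one flag variable and one extra analysis. The sample size does not change. The handling rule is credible only if it is fixed before the data are unblinded.
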